4.5.2 Reassessment of quality of home spirometry

Due to the nature of the home FVC measurements resulting in a highly skewed distribution with high unexpected variability and a number of measurements resulting in physiologically implausible values the home spirometry data was reassessed by an independent and blinded group of experts.

The reassessment of home spirometry data resulted in a flag with 2 categories:

130 = acceptable, 110 = not acceptable.

A comparison between the quality assessments before and after update will be presented by a concordance analysis. In this analysis old assessments with "BOR" are tabulated as non-acceptable quality.

The compliance of home spirometry data will also be assessed by analyzing the number of gaps in daily measurements.

4.5.3 Secondary Efficacy Endpoints

For secondary endpoints, all data from baseline until Week 24 will be taken into account for the statistical analysis. In a similar manner to the primary endpoint data, patients who discontinue early will be analyzed based on the data collected until date of withdrawal from treatment

The secondary efficacy objective for this trial is to evaluate the efficacy of pirfenidone compared with placebo on the basis of the following endpoints:

 Descriptive statistics for values and changes from baseline over time of all spirometry test parameters will be presented.

Pirfenidone — F. Hoffmann-La Roche Ltd

- The decline of FVC in mL measured by spirometry during site (clinic) visits will be compared between the treatment arms in the same fashion as described for the primary endpoint. A Wilcoxon tests was not planned for this endpoint.
- Mean FVC declines and results from Student's t-test by subgroups (for definition see 4.5.6) will be displayed in a forest plot.
- In addition the decline of FVC in mL measured by spirometry during site (clinic) visits will be compared between the treatment arms using a repeated measures mixed effects model. Please refer to Section 4.5.6 for further details.
- The absolute change in percent predicted FVC measured by spirometry during site visits at week 24 will be compared between the treatment arms using a rank analysis of covariance (ANCOVA). Change from baseline will be used as an outcome variable and standardized rank baseline value will be used as a covariate
- Categorical changes in FVC (mL) measured during site (clinic) visits of >5% and >10% will be compared between the treatment arms using a Cochran-Mantel-Haenszel test stratified by concomitant MMF medication use (Yes/No), and the presence/absence of IPAF as defined by the MDT
- Absolute change from baseline to week 24 in percent predicted DLco will be compared between the treatment arms using a rank ANCOVA. Change from baseline to week 24 will be used as an outcome variable and standardized rank baseline value will be used as a covariate
 - A summary table presenting the values of DLco (%) and its change from baseline will be presented over time and by treatment arm.
- The absolute change in 6MWD will be analyzed using a rank ANCOVA model.
 The 6MWD recorded at 24 weeks will be used as an outcome variable and standardized rank baseline 6MWD will be used as a covariate
 - A summary table presenting the 6MWD parameters and their change from baseline will be presented over time and by treatment arm.
- The absolute change in UCSD-SOBQ total score will be analyzed using a rank ANCOVA model. The UCSD-SOBQ total score recorded at 24 weeks will be used as an outcome variable and standardized rank baseline UCSD-SOBQ score will be used as a covariate Please see Section 4.5.5 for further details.
- The absolute change in Leicester Cough Questionnaire total score will be analyzed using a rank ANCOVA model. The Leicester Cough Questionnaire total score recorded at 24 weeks will be used as the outcome variable and standardized rank baseline Leicester Cough Questionnaire total score will be used as a covariate. Please see Section 4.5.5 for further details.

Pirfenidone — F. Hoffmann-La Roche Ltd

- The change in cough visual analog scale will be analyzed using a rank ANCOVA model. The result recorded at 24 weeks will be used as the outcome variable and the standardized rank baseline result will be used as a covariate. Please see Section 4.5.5 for further details.
- The change in total of the SGRQ will be analyzed using a rank ANCOVA model.
 The scores recorded at 24 weeks will be used as outcome variables and the
 standardized rank baseline scores will be used as covariates. Please see Section
 4.5.5 for further details.
- The time from randomization to the first occurrence of all-cause non-elective hospitalization and respiratory non-elective hospitalization will be analyzed using Kaplan-Meier (KM) techniques:
 - KM plots of time to first occurrence of the different events will be provided by treatment arm. Frequencies and percentages of patients with events and patients censored will be provided. Descriptive statistics of KM estimates of the time to first occurrence (weeks) will be presented.
 - Log-rank tests based on the time to the first event will be used to compare the two treatment arms.
 - Hazard ratios and corresponding 95% CI will be calculated by applying Cox-proportional hazard models in which the four groups from the two randomization stratification factors are included in the model.
- The incidence of investigator reported acute exacerbations in the two treatment arms will be compared with Fisher's exact test.
 - o Incidence of, and time to first, investigator-reported acute exacerbations
- Progression free survival (PFS), defined as the time to the first occurrence of a >10% absolute decline in percent predicted FVC, a >50 m decline of 6MWD, or death from any cause, will be analyzed using Kaplan-Meier techniques:
 - KM plots of time to first occurrence of the combined primary efficacy endpoint will be provided by treatment arm.
 - Frequencies and percentages of patients with events and patients censored will be provided. Descriptive statistics of KM estimates of PFS (weeks) will be presented.
 - The PFS of two randomized treatment arms will be compared with a logrank test.
 - Hazard ratios and corresponding 95% CI will be calculated by applying Cox-proportional hazard models.
- An alternative definition of PFS (also in weeks), namely the time to the first occurrence of a >10% relative decline in FVC, non-elective respiratory hospitalization, or death, will be analyzed using Kaplan-Meier techniques as Pirfenidone — F. Hoffmann-La Roche Ltd

- defined for the point above; and the two treatment arms will be compared with a log-rank test. In addition, hazard ratios and corresponding 95% CI will be calculated by applying Cox-proportional hazard models
- Time to death from any cause and time to death from respiratory diseases
 assessed by the SOC "Respiratory, thoracic and mediastinal disorders" (in weeks)
 will be analyzed using Kaplan-Meier techniques as defined above; and the two
 treatment arms will be compared with a log-rank test. In addition, hazard ratios
 and corresponding 95% CI will be calculated by applying Cox-proportional
 hazard models.

For all secondary endpoints p-values will be reported in a descriptive fashion. No multiplicity adjustments for statistical testing will be done.

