4.5.5 Analyses of Patient-Reported Outcomes

Several PRO assessments will be conducted in this trial, including the UCSD-SOBQ, the Leicester Cough Questionnaire, the cough visual analog scale, and the SGRQ.

PRO data will be collected via questionnaires to document the treatment effect and to evaluate the benefit of pirfenidone. The questionnaires, translated into the local language as required, will be completed in their entirety at specified time points during the trial. To ensure instrument validity and that data standards meet health authority requirements, questionnaires will be self-administered before the patient receives any information on disease status and prior to the performance of non-PRO assessments, unless otherwise specified.

St. George's Respiratory Questionnaire (SGRQ)

The St. George's Respiratory Questionnaire (SGRQ) is an index designed to measure and quantifies health-related health status in patients with chronic airflow limitations. The SGRQ is a 50-item questionnaire, addressing the frequency of respiratory symptoms (items 1-8), the patient's current state (sections 9-16). From the 50 items a total score, as well as three component scores (Symptoms, Activities, Impacts) will be derived. The total score ranges from 0, presenting the best possible health status to 100, presenting the worst possible health status.

The change in SGRQ total score will be of primary interest when assessing health-related quality of life (HRQoL).

The analysis of PROs assessed by SGRQ total score and by SGRQ component scores for symptoms, activity, and impacts will be analyzed as follows:

- The absolute score values and changes from baseline for the total and each subscore will be presented descriptively over time by treatment arm.
- Changes from baseline to week 24 or early discontinuation visit will be compared between the treatment arms using a rank ANCOVA with change from baseline as outcome variable and standardized rank baseline value as covariate. This analysis will be done only for the total score.

The SGRQ and the details for calculating the score can be found in Appendix 3.

Pirfenidone — F. Hoffmann-La Roche Ltd

The University of California, San Diego-Shortness of Breath Questionnaire (UCSD-SOBQ)

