4.5.7 Subgroup Analyses

Subgroup analyses will be conducted for the exploratory endpoint, as described in Section 4.5.4. The following subgroups will be based on:

- The four groups resulting from combinations of the two stratification factors:
 - Concomitant MMF treatment (yes/no)
 - o Presence/absence of IPAF as defined by the MDT
- Gender: Male, Female
- Age (years): <65 years, ≥ 65 years
- Percent predicted FVC at Baseline: <65%, ≥65% to < 80%, ≥80%
- Percent predicted DLco at Baseline: <35%, ≥35%
- Body weight: <60 kg, ≥60 kg
- Previous Biopsy (yes/no)

4.5.8 Sensitivity Analyses for missing data

The robustness of the primary method of estimation described above will be explored by a series of sensitivity estimators based on varying assumptions underlying the multiple imputation strategy.

As the primary analysis for this study was performed in March 2019 the number of patients with missing FVC values at week 24 are known. No data was collected after treatment discontinuation.

3 different approaches will be used to evaluate the robustness of the analysis of the secondary endpoint to the missing at random (MAR) assumption.

Due to the low number, deaths and other intercurrent events have not been considered in the multiple imputation analysis.

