4.8 MISSING DATA

With exception of the tipping point analysis described in section 4.5.8, missing data will not be imputed. Other exceptions will be made for the data related to adverse events and concomitant medications as described below.

For adverse events, missing start dates will only be imputed for determination of whether the adverse event is considered to be treatment-emergent or not.

Incomplete or missing onset dates will be imputed to the earliest date possible (using any reliable portions of the onset date that are available). The onset day is considered unreliable if the month or year portions of the date are missing.

In case the month portion of the AE start date is missing, the AE start date will be imputed to the earliest day possible by using the following principles:

- If Treatment Start Date is missing, then the AE Start Date will be imputed as 01-01-YYYY or the earliest date regarding signature of informed consent, screening date or randomization date, whichever is the later one
- When the Treatment Start Date is not missing, and the years of AE Start Date and Treatment Start Date coincide, the AE onset date will be set to the Treatment Start Date
- When the Treatment Start Date is not missing, and the years of the AE Start
 Date and the Treatment Start Date do not coincide, then the AE Start Date will be
 imputed as 01-01-YYYY or the earliest date regarding signature of informed
 consent, screening date or randomization date, whichever is the later one

Pirfenidone — F. Hoffmann-La Roche Ltd

In case the day portion of the AE Start Date is missing, the AE Start Date will be imputed to the earliest day possible as follows:

- If the Treatment Start Date is missing, then the AE Start Date will be imputed as 01-MMM-YYYY or the earliest date regarding signature of informed consent, screening date or randomization date, whichever is the later one
- When the treatment date is not missing, and the years and months from the AE Start Date and the Treatment Start Date coincide, the AE onset date will be set to the Treatment Start Date
- When the Treatment Start Date is not missing, and AE Start Date is after the Treatment Start Date according to the given year or month, then the AE Start Date will be imputed as 01-MMM-YYYY

If the AE stop date is missing, then the event will be assumed to be ongoing and a stop date will not be imputed.

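### The rank ANCOVAs of percent-predicted FVC, DLco and 6MWD need a Week 24 value, so as written they compare completers only, against the SAP's own rule that early stoppers are analysed on data to withdrawal.

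*SAP*

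**What the plan says.** SAP 4.5.3 opens with two general rules for secondary endpoints. The first is "For secondary endpoints, all data from baseline until Week 24 will be taken into account for the statistical analysis". The second is that "patients who discontinue early will be analyzed based on the data collected until date of withdrawal from treatment". SAP 4.5 adds that the efficacy analyses cover the whole ITT population.

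Three rank ANCOVAs in the same section are then tied to Week 24:
- Percent-predicted FVC: "The absolute change in percent predicted FVC measured by spirometry during site visits at week 24 will be compared between the treatment arms".
- DLco: "Change from baseline to week 24 will be used as an outcome variable and standardized rank baseline value will be used as a covariate".
- 6MWD: "The 6MWD recorded at 24 weeks will be used as an outcome variable and standardized rank baseline 6MWD will be used as a covariate".

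On missing values, SAP 4.8 states: "With exception of the tipping point analysis described in section 4.5.8, missing data will not be imputed". The work in 4.5.8 concerns site FVC in mL, not these three endpoints.

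For the SGRQ, UCSD-SOBQ and Leicester totals, SAP 4.5.5 does name a value for early stoppers: "Changes from baseline to week 24 or early discontinuation visit will be compared between the treatment arms using a rank ANCOVA". No matching sentence exists for percent-predicted FVC, DLco or 6MWD.

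**The concern.** A patient with no Week 24 measurement has no outcome in these three analyses, so the two opening rules cannot be met. The unused data exist. Under the schedule of assessments, site spirometry is done at Weeks 4, 8, 12, 16, 20 and 24, and DLco and 6MWD at Weeks 12 and 24.

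The loss may be informative. Patients who stop treatment early end their participation (protocol Appendix 1, footnote b), withdrawals are not replaced, and patients are discontinued when hospitalized for lung transplantation (protocol 4.6.1). If the patients who leave are those declining fastest, and they leave one arm more than the other, the completers' contrast is distorted in a direction that cannot be known in advance. A reader of the report would also take a completer result for the ITT analysis that the SAP describes.

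**Working it through.** **1. Text, side by side**

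| Endpoint | Outcome named in the SAP | Value for early stoppers |
|---|---|---|
| Percent-predicted FVC (4.5.3) | change at Week 24 | none named |
| DLco (4.5.3) | change to Week 24 | none named |
| 6MWD (4.5.3) | Week 24 value | none named |
| SGRQ, UCSD-SOBQ, Leicester (4.5.5) | change to Week 24 | early discontinuation visit |

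A Week 24 outcome with no imputation and no substitute value leaves completers only. No sentence states the exclusion; it follows from these rules together.

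**2. The plan's own figure.** The sample size (SAP 2.3) is for the primary endpoint: difference 85 - 60 = 25 mL, SD 70 mL, two-sided 5%, 80% power.
- Normal approximation: n = 2(1.960 + 0.842)² × (70/25)² = 123.1, so 124 per arm.
- Exact t-test: 125 per arm, with power 80.3%. The stated 125 is reproduced.

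The documents give no dropout rate, and no effect size or SD for the three endpoints here. Everything below is illustrative.

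**3. Fewer patients, no bias.** Assume the same standardized effect (25/70) and equal random loss. Power comes from the noncentral t with noncentrality (25/70)√(m/2), where m is the number of completers per arm.

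| Loss | m | Power |
|---|---|---|
| 0% | 125 | 80.3% |
| 5% | 119 | 78.3% |
| 10% | 112 | 75.8% |
| 15% | 106 | 73.5% |
| 20% | 100 | 71.0% |
| 30% | 88 | 65.4% |

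This is the price of the missing values themselves. An all-visit model recovers only part of it (step 5).

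**4. Bias.**
- *Completer rank ANCOVA with no true effect.* Assumptions: 125 per arm, 3,000 runs, stopping correlated 0.6 with the Week 24 outcome. Two-sided error is 6.0% with 15% informative loss in both arms. It is 12.6% (11.9% favouring pirfenidone) when the worst decliners are lost at 10% on placebo and 20% on pirfenidone. It is 22.9% (22.8% favouring placebo) with 15% informative loss on placebo and 15% random loss on pirfenidone. Stopping here depends partly on values never observed, so an all-visit model would correct it only in part.
- *Completer ANCOVA against a repeated-measures model (arm by visit, baseline by visit), on the mL scale.* Assumptions: 125 per arm, true difference 25 mL, within-visit SD 80 mL, dropout of 10-22% that depends on observed decline and differs by arm. The completer estimate averaged 15-20 mL in some scenarios and about 32 mL in another. The all-visit model averaged 23-27 mL.

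**5. Precision of the same repeated-measures model.** Variance reduction is 1 - (SD of all-visit estimate / SD of completer estimate)².
- FVC: 1 - (17.7/18.5)² = 8%. A separate simulation with 12.8% stopping gave 1 - (17.71/18.05)² = 4%.
- Only Weeks 12 and 24, as for DLco and 6MWD: 1 - (19.0/19.2)² = 2%. Both SDs are rounded, and 1 - (19.05/19.15)² = 1%.

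The gain is therefore about 1-8%.

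**The case against.** **The exclusion is inferred.** SAP 4.5.3 also ties the questionnaire scores to 24 weeks, and 4.5.5 then admits the early discontinuation visit. SAP 4.9 defines an end-of-treatment record that copies early-discontinuation data, and the schedule places spirometry, DLco and 6MWD at that visit. The author may have intended the same here. This stands in part, but none of the three analyses refers to either device. That visit also falls 28 (±5) days after the last dose, outside the efficacy window in SAP 4.2.3, and 4.5.8 says nothing was collected after treatment discontinuation.

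**The stakes are limited.** Secondary p-values are descriptive, and SAP 2.3 calls the trial hypothesis-generating. This stands.

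**A reader might infer that an all-visit analysis brings a large gain in precision.** A random-slope model does: in the simulation with 12.8% stopping its SD was 15.34 mL, against 18.05 mL for completers. But a Week 24 ANCOVA with no dropout at all had SD 16.98 mL, so most of that gain comes from assuming linear decline, not from recovering early stoppers. SAP 4.5.6 already plans that model for site FVC in mL.

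**A reader might infer that deaths go uncounted and must be ranked worst.** The documents do not support this. Deaths count in both PFS definitions and in time to death (4.5.3), and SAP 4.5.8 describes their number as low: "Due to the low number, deaths and other intercurrent events have not been considered in the multiple imputation analysis". Worst ranking turns the endpoint into a composite with death, which is a choice of estimand and not a correction.

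**Conclusion.** The inconsistency is real. As written, the three rank ANCOVAs are completer-only and follow neither the early-stopper rule in SAP 4.5.3 nor the ITT statement in 4.5. The cough VAS analysis is worded for 24 weeks in the same way.

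The consequence is mainly possible bias, in either direction, when stopping depends on decline and differs by arm: about 15-32 mL for completers against 23-27 mL for the all-visit model, where the truth is 25 mL. With similar informative stopping in both arms the problem is small (6.0% error in step 4), and the precision gain is minor.

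These sizes rest on assumed dropout rates, an assumed within-visit SD of 80 mL, and the primary endpoint's effect in mL as a stand-in. They show what could happen, not what did. The point is confined to these analyses: early stoppers still contribute to the site-FVC slopes and mixed model in mL. It merits a supplementary analysis and clearer wording, not replacement of the planned tests.

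**What to change.** For each of the three endpoints:
1. Add a repeated-measures model with arm-by-visit and baseline-by-visit terms on all scheduled visits up to withdrawal: Weeks 4 to 24 for percent-predicted FVC, Weeks 12 and 24 for DLco and 6MWD.
2. Show it beside the rank ANCOVA, and describe the latter as a completer comparison.
3. Label the added model post hoc, because the primary analysis was done in March 2019, before SAP version 3.0 (July 2020).
4. Report by arm how many patients the rank ANCOVA omits, with deaths counted separately.

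Pointing the three ANCOVAs to the early discontinuation visit would not settle the matter alone. SAP 4.2.3, SAP 4.5.8 and the schedule of assessments would first have to be reconciled. Ranking deaths worst could be an optional sensitivity analysis.

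Cost: SAP wording and one standard model per endpoint, with no new data. The model assumes values are missing at random given the observed visits, and it still does not treat death as an outcome.

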6.1 DETERMINATION OF SAMPLE SIZE

The purpose of this trial is hypothesis generation regarding the efficacy of pirfenidone vs. placebo on lung function parameters on the basis of rate of decline in FVC, as measured by daily handheld spirometry.

A total sample size of approximately 250 patients is planned, and patients will be randomized in a 1:1 ratio. The randomization will be stratified by concomitant MMF treatment (yes/no), the presence/absence of IPAF as defined by the MDT.

The planned sample size is based on the statistical hypothesis of the primary endpoint and assumes 80% power and a two-sided significance level of 5% using a student's t-test. It is assumed, after inspection of historical data, that FVC decline in the placebo arm is 85 mL with a common standard deviation of 70 mL, which can be reduced to 60 mL with a common standard deviation of 70 mL in the pirfenidone arm. In this scenario, 125 patients per treatment arm are needed to detect this treatment effect with 80% power.

These assumptions are based upon the following considerations: in IPF, the annual rate of decline of FVC is approximately 200 mL. Owing to the fact that patients with unclassifiable ILD have rates of disease progression in the range of patients with IPF,

albeit with a lower mortality rate (Ryerson et al. 2013), a similar decline rate of 200 mL/year, equivalent to a 100 mL decline over a treatment period of 24 weeks, can be expected. However, a yet unknown proportion of patients in this trial will be treated concomitantly with MMF. In a previous study of CTD-ILD (Fischer et al. 2013), MMF was found to have beneficial effects on lung functions in these patients. While CTD-ILD is a distinct entity from the current trial population, both conditions may share some autoimmune features. Therefore assuming a smaller FVC decline of 85 mL in the placebo arm compared with 60 mL in the pirfenidone arm over the 24-week double-blind treatment period appears justified. In addition, the potential confounding effect of concomitant MMF therapy in these patients justifies stratification to ensure equal distribution of patients who receive and do not receive treatment with MMF.

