2.3 DETERMINATION OF SAMPLE SIZE

The purpose of this trial is hypothesis generation regarding the efficacy of pirfenidone vs. placebo on lung function parameters on the basis of rate of decline in FVC, as measured by daily handheld spirometry.

A total sample size of approximately 250 patients is planned, and patients will be randomized in a 1:1 ratio. The randomization will be stratified by concomitant MMF treatment (yes/no), the presence/absence of IPAF as defined by the MDT.

The planned sample size is based on the statistical hypothesis of the primary endpoint and assumes 80% power and a two-sided significance level of 5% using a student's t-test. It is assumed, after inspection of historical data, that FVC decline in the placebo arm is 85 mL with a common standard deviation of 70 mL, which can be reduced to 60 mL with a common standard deviation of 70 mL in the pirfenidone arm. In this

Pirfenidone — F. Hoffmann-La Roche Ltd

scenario, 125 patients per treatment arm are needed to detect this treatment effect with 80% power.

These assumptions are based upon the following considerations: in IPF, the annual rate of decline of FVC is approximately 200 mL. Owing to the fact that patients with unclassifiable ILD have rates of disease progression in the range of patients with IPF, albeit with a lower mortality rate (Ryerson et al. 2013), a similar decline rate of 200 mL/year, equivalent to a 100 mL decline over a treatment period of 24 weeks, can be expected. However, a yet unknown proportion of patients in this trial will be treated concomitantly with MMF. In a previous study of CTD-ILD (Fischer et al. 2013), MMF was found to have beneficial effects on lung functions in these patients. While CTD-ILD is a distinct entity from the current trial population, both conditions may share some autoimmune features. Therefore, assuming a smaller FVC decline of 85 mL in the placebo arm compared with 60 mL in the pirfenidone arm over the 24-week double-blind treatment period appears justified. In addition, the potential confounding effect of concomitant MMF therapy in these patients justifies stratification to ensure equal distribution of patients who receive and do not receive treatment with MMF.

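### SAP 4.5.3 uses the randomisation strata in some secondary analyses and not others, so the hospitalisation p-value and hazard ratio do not match and related hazard ratios are not comparable

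*SAP*

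**What the plan says.** References are to SAP version 3.0 unless stated otherwise. SAP 3.1 and Protocol 4.2 stratify randomisation by concomitant MMF (yes/no) and IPAF (present/absent), which gives four cells. SAP 2.3 justifies this by the possible confounding effect of MMF.

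SAP 4.5.3 uses those factors in two places. The CMH tests of categorical FVC change are stratified by both. The Cox model for non-elective hospitalisation is specified so that "the four groups from the two randomization stratification factors are included in the model".

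Elsewhere in 4.5.3 they do not appear. For PFS the test is given as "The PFS of two randomized treatment arms will be compared with a logrank test", and the Cox sentence is "Hazard ratios and corresponding 95% CI will be calculated by applying Cox-proportional hazard models", ending there with no strata clause. The alternative PFS and the two death endpoints follow the same pattern. The log-rank tests for hospitalisation also name no strata. In the rank ANCOVAs the only covariate is the ranked baseline: "standardized rank baseline value will be used as a covariate". SAP 4.5.5 repeats this for the patient-reported outcomes.

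No general sentence says that secondary models are adjusted. SAP 4.3 gives the strata a role in a sensitivity analysis of the primary endpoint, and SAP 4.5.6 runs the site-FVC mixed model with and without them. SAP 4.5.3 reports all secondary p-values descriptively, without multiplicity adjustment.

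**The concern.** When randomisation is stratified, the matching analysis conditions on the strata. Here the plan does so for some secondary endpoints and not for others, and gives no reason. Three things follow.

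- For hospitalisation, the reader will see a p-value from an unstratified log-rank test beside a hazard ratio from a Cox model containing the four cells. The two address slightly different contrasts and can disagree near the margin.
- Non-elective respiratory hospitalisation is a component of the alternative PFS. The component's hazard ratio is conditional on strata and the composite's is not, so a difference between them could reflect the adjustment alone.
- If MMF or IPAF predicts outcome, the unstratified tests lose some power and the unadjusted hazard ratios sit closer to 1 than the stratum-conditional ones. With p-values only descriptive, the estimates and intervals are the main output, and those are what the mixed adjustment affects.

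**Working it through.** **1. The plan's own figure.** The inputs are "a two-sided significance level of 5% using a student's t-test", "FVC decline in the placebo arm is 85 mL with a common standard deviation of 70 mL" and "which can be reduced to 60 mL with a common standard deviation of 70 mL in the pirfenidone arm". With a difference of 85 − 60 = 25 mL, the normal approximation gives n = 2 × (1.960 + 0.842)² × 70²/25² = 2 × 7.849 × 7.84 = 123.1, so 124 per arm. The noncentral t gives 124.04, so 125. Power at 125 is 80.6% (normal) or 80.3% (t). The stated 125 per arm, "needed to detect this treatment effect with 80% power", reproduces. It rests on an unadjusted t-test of the primary endpoint, and nothing below changes it.

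**2. Where the strata appear in SAP 4.5.3.**

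| Endpoint | Test | Strata in test | Hazard ratio | Strata in Cox model |
|---|---|---|---|---|
| FVC change >5%, >10% | CMH | yes | – | – |
| Hospitalisation, all-cause and respiratory | log-rank | no | Cox | yes |
| PFS | log-rank | no | Cox | no |
| Alternative PFS | log-rank | no | Cox | no |
| Death, all-cause and respiratory | log-rank | no | Cox | no |
| % predicted FVC, DLco, 6MWD, SOBQ, Leicester, cough VAS, SGRQ total | rank ANCOVA | no | – | – |

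The alternative PFS refers back to the preceding PFS bullet. The death bullet's back-reference attaches to the Kaplan–Meier methods; its own log-rank and Cox sentences carry no strata.

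**3. Size of the effect on log-rank and Cox results.** The documents give no stratum sizes, event rates or prognostic effects, so every input here is an assumption. The simulated design has 250 patients, 1:1 allocation within four cells, exponential times and censoring at 24 weeks. A patient's hazard is λ × r₁^MMF × r₂^IPAF × θ^arm, where λ = −ln(1 − p₀), p₀ is the 24-week risk in the reference cell, and θ is 0.6 (or 1 under the null). The unstratified statistic is Σ(O − E)/√ΣV over the whole sample. The stratified one sums O − E and V within cells first.

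- Set A: MMF 25%, IPAF 20%, p₀ 25%; 2000 runs.
- Set B: MMF 20%, IPAF 15%, p₀ 30% unless shown; 2000 runs.
- Set C: as A, with other prognostic effects; 4000 runs.

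| Set | Hazard ratio of each factor | Power, unstratified | Power, stratified | Difference (points) | Null rejection, unstratified / stratified |
|---|---|---|---|---|---|
| B | 1 | 50.2% | 50.4% | 0.2 | 4.8% / 4.9% |
| C | MMF 0.5, IPAF 1 | 39.4% | 40.0% | 0.6 | 5.1% / 5.3% |
| C | 0.5 | 34.0% | 34.9% | 0.9 | 4.5% / 4.9% |
| C | 1.5 | 49.8% | 50.2% | 0.4 | 4.7% / 5.1% |
| A | 2 | 53% | 56% | 3 | – |
| B | 2 | 59.5% | 61.3% | 1.8 | 4.2% / 5.1% |
| C | 2 | 53.7% | 55.9% | 2.2 | – |
| A | 3 | 55% | 64% | 9 | 3.4% / – |
| B | 3 | 57.6% | 64.7% | 7.1 | 3.8% / 5.6% |
| B, p₀ 10% | 3 | 27.3% | 29.7% | 2.4 | 3.9% / 5.0% |
| B, both factors 50% | 2 | 73.2% | 78.2% | 5.0 | 3.8% / 5.0% |
| B, both factors 50% | 3 | 72.4% | 86.5% | 14.1 | 2.2% / 5.0% |

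With 2000 runs, simulation error is √(0.05 × 0.95/2000) ≈ 0.5 points on null rejection and about 1 point on power. In set B the median hazard ratios (true value 0.60), unstratified and stratified, are 0.604 and 0.595 when each factor doubles the hazard, and 0.630 and 0.600 when each triples it. With both factors at 50% and tripled hazards they are 0.657 and 0.597.

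**4. Rank ANCOVAs.** The same direction is expected, but no size has been calculated. It depends on how much outcome variance MMF and IPAF explain beyond ranked baseline, which the documents do not give.

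**The case against.** The strongest reply is that the unadjusted tests are the pre-specified ones. Protocol 6.4.2 names no strata for any log-rank test, Cox model or rank ANCOVA. SAP version 2.0 of 29 October 2018 (section 4.5.2) already has the same pattern, including the adjusted hospitalisation Cox model. SAP 4.5.8 dates the primary analysis to March 2019, and version 3.0 is dated July 2020. Replacing these tests now would change the plan after results were known. This stands, and it decides how adjusted results may be presented.

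Second, little rides on it. The trial is described as hypothesis-generating, secondary p-values are descriptive, and the large losses need strongly prognostic strata. The documents' only hint of direction is a benefit of MMF in a related disease (SAP 2.3), and in set C a protective MMF effect costs under 1 point. This stands as a limit on size. It does not remove the mismatch between p-value and hazard ratio.

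Third, the unadjusted hazard ratio is a valid marginal estimand, not an error. That is right: lying nearer 1 describes its relation to the stratum-conditional value.

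Fourth, the strata are handled elsewhere: in the FVC mixed models, the CMH tests and the subgroup analyses. That covers FVC, but not PFS or the rank ANCOVAs.

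A reader might infer that the omission was chosen after seeing results. Its presence in version 2.0 rules that out. A reader might also fault the unadjusted primary t-test on the same ground, but SAP 4.3 deliberately places the strata in a sensitivity analysis there.

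**Conclusion.** The inconsistency is plain from the text and worth correcting. Its firm consequence is comparability: the hospitalisation p-value and hazard ratio rest on different adjustments, and the respiratory-hospitalisation hazard ratio does not line up with that of the alternative PFS.

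The loss of efficiency is conditional. With minority strata as in sets A to C, it is about 0–3 power points for modest prognostic effects and about 7–9 points if each factor triples the hazard (2.4 at a 10% event risk). It is larger, at 5 to 14 points, only if both factors are as common as 50%, and nil if the strata are not prognostic. All of this rests on assumed inputs and applies to the log-rank and Cox analyses. The effect on the rank ANCOVAs is unquantified.

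A reader might conclude that the unadjusted analyses are invalid or could produce false positives. The documents and the calculations do not support that: omitting strata that were balanced by design makes a test conservative, if it changes it at all. Nor does any stated sample size or power figure change. For death the case for stratifying is weakest, because SAP 4.5.8 reports few deaths.

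**What to change.** State one rule in SAP 4.5.3:

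- Hospitalisation and both PFS definitions: log-rank tests and Cox models stratified by MMF and IPAF.
- Rank ANCOVAs, in 4.5.3 and 4.5.5: add MMF and IPAF as covariates.
- Sparse cells: a pooling rule written down before the adjusted analyses are run.
- Death: stratify only if event counts allow; otherwise keep the unstratified analysis.
- Source of strata: say whether IxRS or eCRF values are used, since SAP 4.3 plans only a concordance output.

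Report the adjusted results beside the originally specified unadjusted ones, and label them as added after the March 2019 analysis. For hospitalisation, show the hazard ratio both with and without strata, so that each p-value has a matching estimate.

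The cost is a short SAP paragraph, a strata or covariate statement in each program, and extra table columns. No new data are needed. In the scenarios where the strata carried no prognostic information, stratifying cost no measurable power.
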